2.3.4 Confirmation Scans

Verification of Response: To be assigned a status of CR or PR, changes in tumor measurements must be confirmed by consecutive or subsequent repeat assessments that should be performed no less than 28 days after the criteria for response are first met. Subsequent documentation of a CR may provide confirmation of a previously identified CR even with an intervening NE or PR (eg, CR NE CR or CR PR CR). Subsequent documentation of a PR may provide confirmation of a previously identified PR even with an intervening NE or SD (eg, PR NE PR or PR SD PR). However, only one (1) intervening time point will be allowed between PR/CRs for confirmation.

Verification of Progression: Progression of disease should be verified in cases where progression is equivocal. If repeat scans confirm PD, then progression should be declared using the date of the initial scan. If repeat scans do not confirm PD, then the subject is considered to not have progressive disease.

REFERENCES

¹ Eisenhauer EA, Therasse P, Bogaerts J, et al. New response evaluation criteria in solid tumors: revised RECIST guideline (version 1.1). Eur J Cancer 2009; 45: 228-47

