^a If a CR is truly met at first time point, then any disease seen at a subsequent time point, even disease meeting PR criteria relative to baseline, makes the disease PD at that point (since disease must have reappeared after CR). Best response would depend on whether minimum duration for SD was met. However, sometimes 'CR' may be claimed when subsequent scans suggest small lesions were likely still present and in fact the patient had PR, not CR at the first time point. Under these circumstances, the original CR should be changed to PR and the best response is PR.

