##### **4.1.1.1 Primary Definition of Progression-Free Survival (Accounting for Subsequent Therapy)**

[figure not shown]
The primary definition of PFS (PFS truncated at subsequent therapy) is defined as the time between the date of randomization and the date of first documented tumor progression, based on BICR assessments (per RECIST v1.1 criteria), or death due to any cause, whichever occurs first.

Subjects who die without a reported progression will be considered to have progressed on the date of their death. The following censoring rules will be applied for the primary definition of PFS:

- Subjects who did not progress or die will be censored on the date of their last evaluable tumor assessment.
- Subjects who did not have any on study tumor assessments and did not die will be censored on their date of randomization.
- Subjects who receive subsequent anti-cancer therapy prior to documented progression will be censored at the date of the last evaluable tumor assessment conducted on or prior to the date of initiation of the subsequent anti-cancer therapy.
- Subjects who did not have a documented progression and received subsequent anti-cancer therapy will be censored at the date of the last evaluable tumor assessment conducted on or prior to the initiation of the subsequent anti-cancer therapy.

Censoring rules for the primary definition of PFS (PFS truncated at subsequent therapy) are presented as follows in [Figure 4.1.1.1-1](#) and in [Table 4.1.1.1-1](#).

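### Appendix 5 gives conflicting answers for CR–PR–CR when the middle PR reflects disease actually seen: a confirmed CR under section 2.3.4, but progression or a relabelled PR under footnote a to Table 2.3.3-1

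*Protocol*

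**What the plan says.** Three parts of Protocol Appendix 5 bear on a participant read as CR, then PR, then CR.

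- **Section 2.3.4, Confirmation Scans:** "Subsequent documentation of a CR may provide confirmation of a previously identified CR even with an intervening NE or PR". It names CR–PR–CR as an example and adds a limit: "However, only one (1) intervening time point will be allowed between PR/CRs for confirmation". It sets no condition on why the middle scan was a PR.
- **Footnote a to Table 2.3.3-1:** if the first CR was truly met, "any disease seen at a subsequent time point, even disease meeting PR criteria relative to baseline, makes the disease PD at that point". Then "Best response would depend on whether minimum duration for SD was met". If small lesions were probably still present at the first scan, "Under these circumstances, the original CR should be changed to PR and the best response is PR".
- **Table 2.3.2-1, time point response:** with target lesions at CR and no new lesions, the overall response is PR if non-target lesions persist, and also PR if they were not evaluated.

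No text says which of section 2.3.4 and footnote a takes precedence. The SAP does not settle it. Section 4.1.1.1 takes the first BICR-documented RECIST v1.1 progression, or death, as the PFS event. Section 4.1.3 closes the best overall response (BOR) window at documented progression and requires confirmation after at least four weeks, but does not mention this sequence.

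**The concern.** Section 2.3.4 accepts the first CR as real, since a later scan confirms it. A real first CR is exactly the condition under which footnote a calls any disease seen at the next scan progression. The footnote's other branch keeps the participant a responder, but only by withdrawing the first CR. So when disease is seen at the middle scan, neither branch of the footnote gives the confirmed CR that section 2.3.4 gives.

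Progression is the primary endpoint event and also closes the BOR window. The choice of rule can therefore change PFS status or timing, responder status for ORR (third in the Phase 3 hierarchy, SAP 5.2.1), and whether the participant contributes to duration of and time to response. Investigator reads follow the same appendix (Protocol 9.1) and feed the supportive PFS analysis (SAP 7.5.2) and the response concordance table (SAP 7.5.7). The two sets of readers could therefore differ through rule choice alone, although nothing in the documents shows that they did.

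**Working it through.** This is a check of text and logic; the plan states no figure on this point to reproduce.

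**Inputs.** Scans fall at Week 12, then every 8 weeks to Week 52 (Protocol 5.1): Weeks 12, 20, 28 and so on. Confirmation needs at least 28 days (Appendix 5, 2.3.4). The minimum duration for SD is an assumption: by analogy with the Week 6 example in Appendix 5, 2.3.3, it is 12 × 7 − 7 = 77 days.

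**Step 1: does the sequence fit section 2.3.4?** Take CR at Week 12, PR at Week 20, CR at Week 28. The scan gap is 8 × 7 = 56 days and the CR-to-CR gap is 16 × 7 = 112 days, both at least 28. There is one intervening time point, so it qualifies.

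**Step 2: apply each rule, with disease seen at Week 20.**

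| Rule | Sequence as classified | PFS through Week 28 | BOR on these scans | Responder |
|---|---|---|---|---|
| Section 2.3.4 | CR, PR, CR | no event | CR | yes |
| Footnote a, first CR true | CR, PD | event at Week 20 (day 20 × 7 = 140) | SD, as day 84 ≥ 77 (PD if the minimum were not met) | no |
| Footnote a, first CR mistaken | PR, PR, CR | no event | PR | yes |

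Section 2.3.4 and the progression branch differ on both PFS and responder status. Section 2.3.4 and the relabelling branch differ only on CR versus PR.

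**Step 3: how can the middle scan be a PR?** There are three routes in Table 2.3.2-1:

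1. Target lesions at PR: disease is seen.
2. Target lesions at CR, non-target lesions persisting: disease is seen.
3. Target lesions at CR, non-target lesions not evaluated: no disease is seen.

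Footnote a is triggered by disease seen, so it does not reach route 3, and there the later CR can properly confirm the first. The conflict is confined to routes 1 and 2, which section 2.3.4 does not exclude.

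Route 1 need not involve much growth. Suppose a node is the only target lesion with a non-zero measurement and goes from 9 to 10 mm after CR. CR is lost, because CR requires less than 10 mm. The increase is 1 mm, or 1/9 = 11%, short of the ordinary 20% and 5 mm thresholds for progression.

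**Step 4: size.** The documents give neither a CR rate nor a frequency for this sequence. Suppose 1 to 10 participants are affected through the progression branch:

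- Share of PFS events: 1/365 = 0.3% to 10/365 = 2.7%.
- ORR, if all were in one arm of 700/2 = 350: 1/350 = 0.3 to 10/350 = 2.9 percentage points.

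As one illustration inside that range, a CR rate of 10–20% with 3–5% of complete responders showing a single intervening PR gives 700 × 0.10 × 0.03 = 2.1 to 700 × 0.20 × 0.05 = 7 participants. Both rates are assumptions.

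**The case against.** The best defence is that the rules can be read in order. Apply footnote a first: reappeared disease turns the sequence into CR–PD, and a mistaken first CR turns it into PR–PR–CR. What is left as CR–PR–CR is the unevaluated case, which section 2.3.4 then confirms. Section 2.3.4 also says only that a later CR may confirm. This reading is sensible, and the fix adopts it, but no text states that order and the example carries no such limit.

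A second defence is that transient findings are already covered. A new lesion must be unequivocal (Appendix 5, 2.2.2). For equivocal progression, "If repeat scans do not confirm PD, then the subject is considered to not have progressive disease". That stands for equivocal findings. It does not cover disease that has clearly reappeared, and footnote a does not describe its case as equivocal.

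A third is that the BICR charter may fix the rule for the primary endpoint. It may; it is not among the documents. It would not necessarily bind investigator reads.

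Two stronger readings are tempting and fail:

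- A reader might infer that CR–PR–CR can never be a confirmed CR. Route 3 shows that it can.
- A reader might treat the absence of CR from the table's CR-then-PR row as proof. It is not. That table covers two time points, and section 2.3.4 likewise upgrades CR–NE–CR and PR–SD–PR beyond their two-point rows.

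**Conclusion.** The inconsistency is real but narrow. When the middle PR reflects disease seen, two stated rules give different results for the same scans, and nothing ranks them. When it reflects only unevaluated non-target lesions, they agree.

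The effect is probably small. Its frequency is unknown, and the 1-to-10 range is an assumption. PFS and responder status change only under the progression branch; relabelling moves neither. Even under that branch, a participant who later progresses or dies has an event brought forward, not added.

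A reader might infer that the PFS result is biased or could reverse. The documents do not support that: BICR is blinded to arm (Protocol 9.1.2.1), and nothing suggests the sequence falls unevenly between arms. Nor do they say that complete responders drive any late separation of the curves. This is a wording conflict worth correcting, not a threat to the primary conclusion.

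**What to change.** Reconcile Tables 2.3.2-1 and 2.3.3-1 (with footnote a) and section 2.3.4 of Appendix 5:

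- Keep CR–NE–CR as a confirming sequence.
- Limit CR–PR–CR to a middle PR that results solely from unevaluated non-target lesions, with no disease seen.
- State that when disease is seen after a CR, footnote a governs: PD at that scan, or a documented relabelling of the first CR to PR. Equivocal findings go through the existing verification-of-progression rule.
- Apply the same text to BICR and investigator reads.

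Simply deleting PR from the confirmation sentence would be wrong. It would force a complete responder with one unevaluated non-target set into a false progression or a lost CR.

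SAP 5.2.1 records that final PFS was tested on 09MAR2021 and that subject-level unblinding followed, so primary reads should not be re-adjudicated. Instead, state which rule BICR applied, list CR–PR–CR cases by arm, and report PFS and ORR under the other reading as a sensitivity analysis. The listing should flag participants called PD at the second scan who have no later scan. Imaging may stop once BICR confirms progression in someone already off treatment (Protocol 5.1), and the other reading then cannot be fully reconstructed.

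The cost is a short clarification in the appendix, a cross-check against the BICR charter, one listing and one sensitivity run. No new scans or readers are needed.

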APPENDIX 6 ECOG, KARNOFSKY, AND LANSKY PERFORMANCE STATUS SCALES

PERFORMANCE STATUS CRITERIA: ECOG Score	
ECOG (Zubrod)	
Score	Description
0	Fully active; able to carry on all pre-disease performance without restriction
1	Restricted in physically strenuous activity but ambulatory and able to carry out work of a light or sedentary nature, e.g., light house work, office work.
2	Ambulatory and capable of all self care but unable to carry out any work activities; up and about more than 50% of waking hours.
3	Capable of only limited self care; confined to bed or chair more than 50% of waking hours.
4	Completely disabled; cannot carry on any self care; totally confined to bed or chair.

PERFORMANCE STATUS CRITERIA: Karnofsky and Lansky		
Score	Karnofsky Description	Lansky Description
100	Normal; no complaints; no evidence of disease	Fully active, normal
90	Able to carry on normal activity; minor signs or symptoms of disease.	Minor restrictions in physically strenuous activity
80	Normal activity with effort; some signs or symptoms of disease.	Active, but tires more quickly
70	Cares for self; unable to carry on normal activity or to do active work.	Substantial restriction of, and less time spent, in play activity
60	Requires occasional assistance, but is able to care for most of their personal needs.	Out of bed, but minimal active play; keeps busy with quiet activities
50	Requires considerable assistance and frequent medical care.	Gets dressed, but inactive much of day; no active play, able to participate in quiet play
40	Disabled; requires special care and assistance.	Mostly in bed; participates in some quiet activities
30	Severely disabled; hospital admission is indicated although death not imminent.	In bed; needs assistance even for quiet play
20	Very sick; hospital admission necessary; active supportive treatment necessary.	Often sleeping; play limited to passive activities
10	Moribund; fatal processes progressing rapidly.	No play; does not get out of bed
0	Dead	Unresponsive

APPENDIX 7 AJCC MELANOMA STAGING (CANCER STAGING MANUAL 8TH EDITION)

[From AJCC Cancer Staging Manual, 8th Edition. Amin MB, Edge S, Greene F, Byrd DR, Brookland RK, Washington MK, et al. editors. Springer International Publishing. 2017 (pages 577 & 578)]

Definition of Primary Tumor (T)

T Category	Thickness	Ulceration Status
TX: primary tumor thickness cannot be assessed (e.g., diagnosis by curettage)	Not applicable	Not applicable
T0: no evidence of primary tumor (e.g., unknown primary or completely regressed melanoma)	Not applicable	Not applicable
Tis (melanoma in situ)	Not applicable	Not applicable
T1	≤1.0 mm	Unknown or unspecified
T1a	<0.8 mm	Without ulceration
T1b	<0.8 mm 0.8-1.0 mm	With ulceration With or without ulceration
T2	>1.0-2.0 mm	Unknown or unspecified
T2a	>1.0-2.0 mm	Without ulceration
T2b	>1.0-2.0 mm	With ulceration
T3	>2.0-4.0 mm	Unknown or unspecified
T3a	>2.0-4.0 mm	Without ulceration
T3b	>2.0-4.0 mm	With ulceration
T4	>4.0 mm	Unknown or unspecified
T4a	>4.0 mm	Without ulceration
T4b	>4.0 mm	With ulceration

Definition of Distant Metastasis (M)

M Category	Anatomic site	LDH level
M0	No evidence of distant metastasis	Not applicable
M1	Evidence of distant metastasis	See below
M1a	Distant metastasis to skin, soft tissue including muscle, and/or non-regional lymph node	Not recorded or unspecified
M1a(0)		Not elevated
M1a(1)		Elevated
M1b	Distant metastasis to lung with or without M1a sites of disease	Not recorded or unspecified
M1b(0)		Not elevated
M1b(1)		Elevated
M1c	Distant metastasis to non-CNS visceral sites with or without M1a or M1b sites of disease	Not recorded or unspecified
M1c(0)		Not elevated
M1c(1)		Elevated
M1d	Distant metastasis to CNS with or without M1a, M1b, or M1c sites of disease	Not recorded or unspecified
M1d(0)		Not elevated
M1d(1)		Elevated
Suffixes for M category: (0) LDH not elevated; (1) LDH elevated. No suffix is used if LDH is not recorded or is unspecified.		

Definition of Regional Lymph Node (N)

N Category	Number of tumor-involved regional lymph nodes	Presence of in-transit, satellite, or microsatellite metastases
NX	Regional nodes not assessed (e.g., SLN biopsy not performed, regional nodes previously removed for another reason) Exception: pathological N category is not required for T1 melanomas, use cN	No
N0	No regional metastases detected	No
N1	One tumor-involved node or in-transit, satellite, and/or microsatellite metastases with no tumor-involved nodes	
N1a	One clinically occult (i.e., detected by SLN biopsy)	No
N1b	One clinically detected	No
N1c	No regional lymph node disease	Yes
N2	Two or three tumor-involved nodes or in-transit, satellite, and/or microsatellite metastases with one tumor-involved node	
N2a	Two or three clinically occult (i.e., detected by SLN biopsy)	No
N2b	Two or three, at least one of which was clinically detected	No
N2c	One clinically occult or clinically detected	Yes
N3	Four or more tumor-involved nodes or in-transit, satellite, or microsatellite metastases with two or more tumor-involved nodes, or any number of matted nodes with or without in-transit, satellite, and/or microsatellite metastases	
N3a	Four or more clinically occult (i.e., detected by SLN biopsy)	No
N3b	Four or more, at least one of which was clinically detected, or presence any number of matted nodes	No
N3c	Two or more clinically occult or clinically detected, and/or presence any number of matted nodes	Yes

AJCC Prognostic Stage Groups

Clinical (cTNM)

Clinical stage includes microstaging of the primary melanoma and clinical/radiologic/biopsy evaluation for metastases. By convention, clinical staging should be used after biopsy of the primary melanoma, with clinical assessment for regional and distant metastases. Note that pathological assessment of the primary melanoma is used for both clinical and pathological classification. Diagnostic biopsies to evaluate possible regional and/or distant metastasis also are included. Note there is only one stage group for clinical Stage III melanoma.

When T is....	And N is.....	And M is....	The clinical stage is...
Tis	N0	M0	0
T1a	N0	M0	IA
T1b	N0	M0	IB
T2a	N0	M0	IB
T2b	N0	M0	IIA
T3a	N0	M0	IIA
T3b	N0	M0	IIB
T4a	N0	M0	IIB
T4b	N0	M0	IIC
Any T, Tis	≥N1	M0	III
Any T	Any N	M1	IV

PATHOLOGICAL (pTNM)

Pathological staging includes microstaging of the primary melanoma, including any additional staging information from the wide excision (surgical) specimen that constitutes primary tumor surgical treatment and pathological information about the regional lymph nodes after SLN biopsy or therapeutic lymph node dissection for clinically evident regional lymph node disease.

When T is....	And N is....	And M is....	The pathological stage is...
Tis	N0	M0	0
T1a	N0	M0	IA
T1b	N0	M0	IA
T2a	N0	M0	IB
T2b	N0	M0	IIA
T3a	N0	M0	IIA
T3b	N0	M0	IIB
T4a	N0	M0	IIB
T4b	N0	M0	IIC
T0	N1b, N1c	M0	IIIB
T0	N2b, N2c, N3b or N3c	M0	IIIC
T1a/b-T2a	N1a-N2a	M0	IIIA
T1a/b-T2a	N1b/c or N2b	M0	IIIB
T2b/T3a	N1a-N2b	M0	IIIB
T1a-T3a	N2c or N3a/b/c	M0	IIIC
T3b/T4a	Any N \geq N1	M0	IIIC
T4b	N1a-N2c	M0	IIIC
T4b	N3a/b/c	M0	IIID
Ant T, Tis	Any N	M1	IV
Pathological Stage 0 (melanoma in situ) and T1 do not require pathological evaluation of lymph nodes to complete pathological staging; use cN information to assign their pathological stage.			

APPENDIX 8 COUNTRY SPECIFIC REQUIREMENTS

Argentina, Czech Republic, Germany, Peru and Any Other Countries Where Exclusion of HIV Positive Participants Is Locally Mandated

	Country-specific language
Section 2 Flow Chart/Time and Events Schedule, Table 2-1: Screening Assessments- Laboratory Tests	Add “HIV” to the list of laboratory tests
Section 6.2 Exclusion Criteria, Exclusion criterion 3j	“Known history of testing positive for human immunodeficiency virus (HIV) or known acquired immunodeficiency syndrome (AIDS)”to be replaced with “Positive test for HIV”.

APPENDIX 9 MANAGEMENT ALGORITHMS FOR IMMUNO-ONCOLOGY AGENTS

These general guidelines constitute guidance to the Investigator and may be supplemented by discussions with the Medical Monitor representing the Sponsor. The guidance applies to all immuno-oncology agents and regimens.

A general principle is that differential diagnoses should be diligently evaluated according to standard medical practice. Non-inflammatory etiologies should be considered and appropriately treated.

[figure not shown]
Corticosteroids are a primary therapy for immuno-oncology drug-related adverse events. The oral equivalent of the recommended IV doses may be considered for ambulatory patients with low-grade toxicity. The lower bioavailability of oral corticosteroids should be taken into account when switching to the equivalent dose of oral corticosteroids.

Consultation with a medical or surgical specialist, especially prior to an invasive diagnostic or therapeutic procedure, is recommended.

The frequency and severity of the related adverse events covered by these algorithms will depend on the immuno-oncology agent or regimen being used.

GI Adverse Event Management Algorithm

Rule out non-inflammatory causes. If non-inflammatory cause is identified, treat accordingly and continue I-O therapy.
Opiates/narcotics may mask symptoms of perforation. Infliximab should not be used in cases of perforation or sepsis.

Patients on IV steroids may be switched to an equivalent dose of oral corticosteroids (eg, prednisone) at start of tapering or earlier, after sustained clinical improvement is observed. Lower bioavailability of oral corticosteroids should be taken into account when switching to the equivalent dose of oral corticosteroids.

[figure not shown]
* Discontinue for Grade 4 diarrhea or colitis. For Grade 3 diarrhea or colitis, 1) Nivolumab monotherapy: Nivolumab can be delayed. 2) Nivolumab+ Ipilimumab combination: Ipilimumab should be discontinued while nivolumab can be delayed. Nivolumab monotherapy can be resumed when symptoms improve to Grade 1. Please refer to protocol for dose delay and discontinue criteria for other combinations.

28-Sep-2020

Renal Adverse Event Management Algorithm

Rule out non-inflammatory causes. If non-inflammatory cause, treat accordingly and continue I-O therapy.

[figure not shown]

Patients on IV steroids may be switched to an equivalent dose of oral corticosteroids (eg, prednisone) at start of tapering or earlier, after sustained clinical improvement is observed. Lower bioavailability of oral corticosteroids should be taken into account when switching to the equivalent dose of oral corticosteroids.

28-Sep-2020

Pulmonary Adverse Event Management Algorithm

Rule out non-inflammatory causes. If non-inflammatory cause, treat accordingly and continue I-O therapy.
Evaluate with imaging and pulmonary consultation.

[figure not shown]
Patients on IV steroids may be switched to an equivalent dose of oral corticosteroids (eg, prednisone) at start of tapering or earlier, after sustained clinical improvement is observed. Lower bioavailability of oral corticosteroids should be taken into account when switching to the equivalent dose of oral corticosteroids.

28-Sep-2020

Hepatic Adverse Event Management Algorithm

Rule out non-inflammatory causes. If non-inflammatory cause, treat accordingly and continue I-O therapy.
Consider imaging for obstruction.

Patients on IV steroids may be switched to an equivalent dose of oral corticosteroids (e.g. prednisone) at start of tapering or earlier, after sustained clinical improvement is observed. Lower bioavailability of oral corticosteroids should be taken into account when switching to the equivalent dose of oral corticosteroids.

^Λ Please refer to protocol dose delay and discontinue criteria for specific details.

[figure not shown]
*The recommended starting dose for AST or ALT > 20 x ULN or bilirubin >10 x ULN is 2 mg/kg/day methylprednisolone IV.

28-Sep-2020

Endocrinopathy Adverse Event Management Algorithm

Rule out non-inflammatory causes. If non-inflammatory cause, treat accordingly and continue I-O therapy.
Consider visual field testing, endocrinology consultation, and imaging.

[figure not shown]
Patients on IV steroids may be switched to an equivalent dose of oral corticosteroids (eg, prednisone) at start of tapering or earlier, after sustained clinical improvement is observed. Lower bioavailability of oral corticosteroids should be taken into account when switching to the equivalent dose of oral corticosteroids.

28-Sep-2020

Skin Adverse Event Management Algorithm

Rule out non-inflammatory causes. If non-inflammatory cause, treat accordingly and continue I-O therapy.

Patients on IV steroids may be switched to an equivalent dose of oral corticosteroids (e.g. prednisone) at start of tapering or earlier, after sustained clinical improvement is observed. Lower bioavailability of oral corticosteroids should be taken into account when switching to the equivalent dose of oral corticosteroids.

*Refer to NCI CTCAE v5 for term-specific grading criteria.

[figure not shown]
^If Steven-Johnson Syndrome (SJS), toxic epidermal necrosis (TEN), Drug Reaction with Eosinophilia and Systemic Symptoms (DRESS) is suspected, withhold I-O therapy and refer patient for specialized care for assessment and treatment. If SJS, TEN, or DRESS is diagnosed, permanently discontinue I-O therapy.

28-Sep-2020

Neurological Adverse Event Management Algorithm

Rule out non-inflammatory causes. If non-inflammatory cause, treat accordingly and continue I-O therapy.

[figure not shown]
Patients on IV steroids may be switched to an equivalent dose of oral corticosteroids (eg. prednisone) at start of tapering or earlier, after sustained clinical improvement is observed. Lower bioavailability of oral corticosteroids should be taken into account when switching to the equivalent dose of oral corticosteroids.

[^]Discontinue for any grade myasthenia gravis, Guillain-Barre syndrome, treatment-related myelitis, or encephalitis.

28-Sep-2020

Relatlimab Myocarditis Adverse Event Management Algorithm

For the protocols under CTCAE version 5.0. Patients on IV steroids may be switched to an equivalent dose of oral corticosteroids (eg, prednisone) at start of tapering or earlier, once sustained clinical improvement is observed. Lower bioavailability of oral corticosteroids should be taken into account when switching to the equivalent dose of oral corticosteroids. Prophylactic antibiotics should be considered in the setting of ongoing immunosuppression.

ATG = anti-thymocyte globulin; BNP = B-type natriuretic peptide; ECG = electrocardiogram; IV = intravenous; MRI = magnetic resonance imaging

11-Sep-2020

